2.1 Risk / Benefit Assessment

Side effects associated with taking the study medication

Likely to occur:

- Oral methamphetamine is a stimulant and may cause increased blood pressure, heart rate, and palpitations (noticeably rapid, strong, or irregular heartbeats).

Less likely to occur:

- In some cases, oral methamphetamine can cause some dizziness, headache, insomnia, elevated mood, depressed mood, restlessness, diarrhea, constipation, unpleasant taste, dry mouth, and tremor (hands shaking).

Very unlikely to occur:

- At very high doses (much higher than the doses being given in this study) and if taken for prolonged periods of time (e.g., weeks to months to years), oral methamphetamine can lead to a substance use disorder, exacerbation of preexisting abnormal movements (called “tics”), psychotic symptoms (hearing and seeing things that are not actually there), frequent erections, impotence, and changes in libido.

Side effects associated with taking placebo

Very unlikely to occur:

- In order to make the placebo appear similar to the study medication, the pills will be crushed and placed in a capsule. For the placebo phase, cornstarch will be placed inside the capsule. Therefore, individuals who have an allergy to cornstarch may be at risk of an allergic reaction when taking placebo and should notify the study investigator if they have a known allergy to cornstarch.

HIV viral load and resistance to antiretroviral therapy risks

Very unlikely to occur:

- We will be measuring the amount of viral RNA that increases after the study drug. This does not necessarily mean that there is an increase in the amount of circulating HIV. Nonetheless, since there is a very small chance that there could be an in circulating virus, there would be a theoretical risk of developing resistance to antiretroviral therapy. The likelihood of this is extremely low, given that participants will only be given one day of a single day's maximum pediatric dose of the study medication, and if the study medication induces viral rebound, the predicted increases in HIV in the blood is extremely small. For these reasons, individuals can only participate in this study if there are alternate ART regimens available in the rare event that their current ART regimen is compromised as a result of this study. During the study, participants will have their HIV viral load followed closely (at screening, baseline, and on days 2, and 31 of each treatment arm).

Drug-drug interactions

Very unlikely to occur:

- We believe that the likelihood of this is extremely low, given that participants will only be given one day of a low dose of the study medication. Strict

criteria for potential medications that could interact with the study drug will be used, and the following medications are not allowed during the study because of potential interactions with the study medication: acebropyline, iobenguane, isocarboxazid, methylene blue, moclobemide, phenylzine, procarbazine, rasagiline, safinamide, selegiline, tranylcypromine, asunaprevir, bupropion, topical cocaine, fluoxetine, iohexol, linezolid, paroxetine, potassium citrate, quinidine, sodium bicarbonate, sodium citrate, sodium lactate, tipranavir, and tromethamine. This is because the study medication may alter metabolism of the drugs.

Side effects of taking your blood sample (phlebotomy)

Likely to occur:

- Drawing blood from a vein may cause some discomfort, bleeding or bruising where the needle enters the skin, and rarely, fainting or infection may occur. Up to a total of 795 milliliters (about 53 tablespoons) will be collected during the course of this study, which has been carefully calculated over the 146 days of the study to ensure that blood levels are not below American Red Cross Guidelines.
- Less likely to occur:
 - Less common symptoms include lightheadedness, dizziness, fainting and nausea. Symptoms of anemia include tiredness, weakness and dizziness. A CBC with differential will be collected at all visits from screening through day 31 of each treatment arm. If the investigator feels that there is a significant risk for anemia, the amount of blood collected will be reduced. If the participant's hemoglobin falls below 10 g/dl or the hematocrit falls below 27%, there will be a 5 ml (1 teaspoon) blood draw check the hemoglobin and hematocrit. No more blood will drawn until the participant's hemoglobin rises above 10 g/dl or hematocrit rises above 27%

Confidentiality

Participation in research may involve a loss of privacy; however, your records will be handled as confidentially as possible. All study questionnaires and research samples will be coded with a study ID. No personal identifiers such as your name will be used for stored specimens. [name] and the research staff as well as the UCSF Committee on Human Research will have access to your study records and test results. No individual identities will be used in any reports or publications that may result from this study. California regulations require laboratories to report new cases of tuberculosis, hepatitis B, and hepatitis C infection to the county public health department. The reports include the patient's name, social security number, and other identifying information. Information about these new infections is used to track these diseases statewide and nationwide. Other than this required reporting, your results will be treated confidentially by the study staff. Personally identifying information will not be reported to other departments or agencies.

Risk of genetic testing

Genetic information that results from this study does not have medical or treatment importance at this time. However, there is a risk that information about taking part in a

genetic study may influence insurance companies and/or employers regarding a participant's health. To further safeguard participant privacy, genetic information obtained in this study will not be placed in his/her medical record.

Effect on participating in other studies

Every research study has different requirements for participation, which are known as eligibility criteria. If a participant agrees to take part in this study, the procedures required for this study may make him/her not eligible to participate in other studies for a period of time. How long that period of time is determined by the other study.

Reproductive risks

Methamphetamine is classified as FDA pregnancy risk category C. There are no adequate and well-controlled studies of methamphetamine use in pregnant women. Since there are limited data on pregnancy risk related to methamphetamine given for a single day at the FDA-approved pediatric daily dose, we will take precautions around potential pregnancy during the trial. According to the manufacturer, amphetamines are excreted into breast milk, and women who are taking amphetamines should refrain from nursing. The effect of stimulant medication exposure via breast milk on the neurological development of the infant has not been well studied. Breast milk concentrations in one woman taking 20 mg daily of racemic amphetamine ranged from 55 to 138 ng/mL with milk to plasma ratios of 2.8 to 7.5. For this reason, if a participant is breast-feeding, pregnant or plan to become pregnant, she cannot participate in this clinical trial. Female participants will be asked to take a pregnancy test at the beginning of the clinical trial and before each dose of investigational products in order to determine pregnancy. If a participant is able to become pregnant, two of the following forms of birth control are required, one of which must be condoms or a diaphragm or cervical cap:

- Condoms (male or female) with or without a spermicidal agent
- Diaphragm or cervical cap with spermicide
- Intrauterine device (IUD) with published data showing that expected failure rate is < 1% per year
- Tubal ligation
- Hormone-based contraceptive such as oral birth control pills

Participants are advised that even if they use acceptable forms of birth control during the clinical trial, there is a chance she could become pregnant. If she does become pregnant during the clinical trial she is advised:

- To call/notify the study doctor immediately
- To consult an obstetrician or maternal-fetal specialist
- That she will not be given any additional investigational products
- That she will be followed to determine the pregnancy outcome

If the participant is a male who is sexually active with a woman capable of becoming

pregnant, he must agree to use a medically accepted form of birth control during the

course of this research study. He is advised to inform his partner of the potential harm to an unborn child. The partner needs to know that if she does become pregnant during the study:

- The participant will need to call/notify the study doctor immediately
- She will need to consult an obstetrician or maternal-fetal specialist
- Study staff will ask for her permission to collect information about the pregnancy and the health of the baby. This includes information related to the pregnancy/delivery and obstetrical history.

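### Section 2.1: the conditions for stopping and restarting blood draws overlap when read literally, so drawing could resume while the triggering value is still low

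*Combined protocol and SAP*

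**What the plan says.** The rule is in the phlebotomy part of section 2.1 (Risk / Benefit Assessment) of the combined protocol and SAP. It has three parts.

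- **Trigger.** The precaution starts if the participant's "hemoglobin falls below 10 g/dl or the hematocrit falls below 27" percent.
- **Action.** On that result, "there will be a 5 ml (1 teaspoon) blood draw check the hemoglobin and hematocrit", and no further blood is taken for the time being.
- **Release.** Drawing may resume when the participant's "hemoglobin rises above 10 g/dl or hematocrit rises above 27" percent.

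Two other provisions stand next to it. "A CBC with differential will be collected at all visits from screening through day 31 of each treatment arm", so paired hemoglobin and hematocrit values will be available. If the investigator sees a significant risk of anemia, "the amount of blood collected will be reduced". On the planned volume, the section says: "Up to a total of 795 milliliters (about 53 tablespoons) will be collected during the course of this study".

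No other section restates or clarifies the trigger or the release. Section 9.2.1 lists the blood count without limits, and section 10.4 (Criteria for Discontinuation) has no specific hemoglobin or hematocrit limit.

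**The concern.** A hold that starts when either of two values is low does not fit well with a release that is met when either of the two is acceptable. Under these two conditions a participant can be inside the hold and eligible for release on the same pair of results. The text does not say that the value that fell must be the one that recovers, or that both must be above their limits.

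What is at stake is participant safety and uniform conduct. This is the only numeric hold on blood drawing during follow-up in the documents, in a study that plans up to 795 mL over 146 days. Two staff members could apply it to the same laboratory report and reach opposite decisions. No endpoint, analysis or sample-size figure depends on it.

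**Working it through.** **Inputs.** Trigger and release limits: 10 g/dl and 27%, both from section 2.1. The ratio of hemoglobin (Hb) to hematocrit (Hct) is not in the documents. It is an assumption here, shown over 30 to 36 g/dL. The plan states no figure of its own to reproduce.

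**Step 1: logic, no assumption needed.**

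- Trigger T: Hb < 10 or Hct < 27.
- Release R: Hb > 10 or Hct > 27.
- T and R are both true whenever one value is below its limit and the other above it.
- Once triggered, the hold lasts only while Hb ≤ 10 and Hct ≤ 27 together.

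| Hb (g/dl) | Hct (%) | Trigger met | Release met |
|---|---|---|---|
| 9.5 | 28 | yes | yes |
| 10.5 | 26.5 | yes | yes |
| 9.5 | 26.5 | yes | no |
| 8.9 | 26.7 | yes | no |
| 10.5 | 31.5 | no | not applicable |

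The first two rows show the overlap. The next two show that the hold works when both values are low.

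**Step 2: width of the overlap, on an assumed ratio.** Write r = Hb / (Hct/100), in g/dL. A hematocrit of 27% then corresponds to Hb = 0.27 × r. The two limits coincide when 0.27 × r = 10, that is r = 10 / 0.27 = 37.0 g/dL. Below that ratio, a sample with Hb between 0.27 × r and 10 has Hct above 27%, so it meets both conditions.

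| Assumed r (g/dL) | Lower end of overlap, 0.27 × r (g/dl) | Width, 10 − 0.27 × r (g/dl) |
|---|---|---|
| 30 | 8.10 | 1.90 |
| 32 | 8.64 | 1.36 |
| 33.3 | 9.00 | 1.00 |
| 34 | 9.18 | 0.82 |
| 36 | 9.72 | 0.28 |

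**Step 3: what this means for the hemoglobin limit.** At any r below 37.0, Hct ≤ 27% already implies Hb < 10. The hold therefore persists exactly when Hct ≤ 27%, and Hb < 10 adds nothing to keeping it in place. It still prompts the recheck.

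The pair 10.5 / 26.5 implies r = 10.5 / 0.265 = 39.6, outside the assumed range. It illustrates the logic rather than a typical sample. The pair 9.5 / 28 implies r = 9.5 / 0.28 = 33.9, inside the range.

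**The case against.** **The value that fell is the one that must rise.** The release speaks of values rising, in parallel with values falling in the trigger. On that reading a hematocrit that never dropped has not risen, and 9.5 / 28 would not lift the hold. This is a plausible intention, but the text does not state it, and a hematocrit of 28 is literally above the release limit. The objection shows that the wording can be read in two ways; it does not settle which is meant.

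**There is a recheck between trigger and release.** This stands. Release may be judged on a second sample, so a hold is not necessarily started and lifted by one tube of blood. But if the recheck returns a similar pair, the release is met with the triggering value still low.

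**Other safeguards exist.** This also stands. There is a blood count at every visit from screening through day 31 of each arm, discretion to reduce the volume, and discretion to stop study treatment (section 11.1). Known anemia is excluded at entry (hematocrit below 34 for males, below 32 for females, in both the synopsis and section 6.3). A reader might infer that the anemia protection as a whole is void; the documents do not support that.

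**The band may rarely be reached.** The synopsis excludes a screening hemoglobin below 12.5 g/dL. Assume a blood volume of 4 to 5 L (not in the documents) and no red-cell replacement. Losing all 795 mL then leaves 12.5 × (1 − 795/4000) = 10.02 to 12.5 × (1 − 795/5000) = 10.51 g/dl, just above the trigger. This is a fair point on frequency, with a limit: section 6.3 omits the 12.5 criterion. Under its hematocrit limits alone, and assuming r = 33.3 g/dL, entry at about 0.32 × 33.3 = 10.7 or 0.34 × 33.3 = 11.3 g/dl would be possible, close to the trigger. The documents give no basis for how often the overlap would occur among 10 participants.

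**Conclusion.** The overlap is real and follows from the text alone: any pair with one value below its limit and the other above it satisfies both the hold and its release. Its width depends on a ratio that the documents do not give. Over an assumed 30 to 36 g/dL, the lower end of the overlap lies between 8.1 and 9.7 g/dl and the upper end is 10 g/dl, so the width runs from 1.90 down to 0.28 g/dl. Below 37.0 g/dL the hemoglobin limit does not by itself sustain a hold.

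Three stronger readings are tempting and are not supported. First, that the rule never holds: it does whenever both values are at or below their limits and at least one is below. Second, that the hemoglobin limit has no effect: it still prompts the recheck. Third, that the working limit has dropped to 9 g/dl: that figure is only the result at one assumed ratio, 33.3 g/dL. The point is an inconsistency in the wording of a safety rule, worth correcting because the correction is easy. It does not threaten the trial's conclusions.

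**What to change.** The investigators should reconcile the trigger and release sentences in section 2.1 so that no set of values satisfies both, and state the rule they intend. That statement should make clear which value or values must recover and whether release is judged on the recheck sample. No threshold or rule is proposed here; that is a clinical decision for the study team.

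They should also check whether any participant-facing text repeats the wording. The consent pages were not available for this review, so nothing is asserted about them.

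The cost is a short wording amendment, with the prior written IRB approval that section 16.1 requires. Whether more or fewer research draws would be skipped depends on the rule chosen.

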3 STUDY OBJECTIVES

3.1 Primary Objective

Determine whether short-term MA exposure increases residual viral production, markers of inflammation (plasma cytokine levels), and cell surface immune marker expression (flow cytometry) in blood.

3.2 Secondary Objectives

The second objective is to identify differentially expressed genes and proteins in blood, before and after short-term MA administration.

The third objective is to determine whether trace amine receptor 1 (TAAR1) signaling mediates observed effects of MA administration.

4 STUDY DESIGN

4.1 Study Overview

This is a phase IV open label randomized, double-blinded, placebo-controlled crossover study. A placebo treatment arm will be assigned to participants in a randomized crossover design. HIV+ ART-suppressed individuals with no prior history of MA use disorder will be administered 10mg oral methamphetamine hydrochloride (Desoxyn®), followed by 15 mg methamphetamine hydrochloride two hours later, for a total of 25mg in one 24-hour period (the maximum FDA approved daily dose for the treatment of childhood obesity). Participants will complete the study twice (once on a placebo treatment arm and once with the Desoxyn® treatment arm). Which treatment arm occurs first will be randomly assigned and will include a 31-day washout period between the two phases. The placebo is similar in appearance, consistency, and taste to methamphetamine hydrochloride tablets, USP (Desoxyn®), without any known drug-drug interactions (e.g., changes in pH balance that might affect drug absorption) with HIV antiretroviral therapy.

5 CRITERIA FOR EVALUATION

5.1 Primary Efficacy Endpoint

There is not a primary efficacy endpoint aim for this phase IV study, though we will be reporting changes in measures of HIV transcription, immune activation, and inflammation.

5.2 Safety Evaluations

Incidence and nature of adverse events

5.3 Other Evaluations (include only if applicable)

PBMCs will be collected for gene expression analyses. Plasma samples will be stored for future PK analyses

6 PARTICIPANT SELECTION

6.1 Study Population

1. HIV-positive adults age ≥ 18 years and ≤ 65 years suppressed on long-term stable antiretroviral therapy, with adequate organ function (per criteria listed below).

6.2 Inclusion Criteria

2. Willing and able to provide written informed consent
3. Male or female, age ≥ 18 years and ≤ 65 years
4. Laboratory confirmed documentation of HIV-1 infection.
5. Continuous therapy with a DHHS recommended/alternative combination ART for least 12 months (at least 3 agents) at study entry with no regimen changes in the preceding 12 weeks
6. Maintenance of undetectable plasma HIV-1 RNA below the limit of quantification for at least 12 months. Episodes of single HIV plasma RNA 50-500 copies/ml will not exclude participation if subsequent HIV plasma RNA is below the limit of assay detection.
7. No plans to modify ART during the study period (146 days, or approximately 5 months)
8. Participant and partner(s) are willing to use two forms of contraception throughout the study period as well as up to 60 days after the last day of study completion.
9. Ability and availability to participate in the full 146 days of the study (approximately 5 month) and maintain the inclusion/exclusion criteria
10. No current or prior history of methamphetamine (MA) use disorder by DSM-5 diagnostic criteria. Participants may have a prior history of taking prescription

medications containing amphetamines-type stimulants such as Adderall® or Dexedrine® or Ritalin for the treatment of conditions such as attention deficit hyperactivity disorder as long as the participant has not taken these medications in the last 12 months or plans to take these medications during the entire study period.

6.3 Exclusion Criteria

11. History of methamphetamine (“meth”) use disorder by DSM-5 diagnostic criteria using the 11-symptom checklist.
12. Evidence of MA use other than due to the administered oral methamphetamine study drug, based on urine, hair, or serum MA measurements collected at baseline and follow-up study visits.
13. Current use of prescription medications containing amphetamine-type stimulants (e.g., Adderall®, Dexedrine®, Ritalin, etc.) within the past 1 year.
14. Sensitivity or allergy to amphetamine-type stimulants
15. Current use of any other “psychoactive” drug within the last 1 month. These include cocaine, ecstasy, LSD, mushrooms, or other recreational drugs – but cannabis, nicotine or caffeine use is ok.
16. Use of illicit opioids (heroin, fentanyl) – but ok if use of prescription opioid agonists with known prescribed doses, such as methadone, hydrocodone (Norco®), buprenorphine/naloxone (Suboxone®), oxycodone (Oxycontin®), hydromorphone (Dilaudid®) within the past 3 months by self-report and/or urine qualitative screening.
17. Current moderate to severe use of alcohol use disorder (DSM-5 criteria) as this might put patient at risk of withdrawal during the study.
18. Recent use within the last month of the following medications given potential interactions with oral methamphetamine: acebromphyline, iobenguane, isocarboxazid, methylene blue, moclobemide, phenylzine, procarbazine, rasagiline, safinamide, selegiline, tranylcypromine, asunaprevir, bupropion, topical cocaine, fluoxetine, iohexol, linezolid, paroxetine, potassium citrate, quinidine, sodium bicarbonate, sodium citrate, sodium lactate, tipranavir, and tromethamine.
19. Recent hospitalization in the last 90 days.
20. Recent infection in the last 90 days requiring prolonged (e.g., >3 weeks) of systemic intravenous antibiotics.
21. Known anemia (HIV+ males Hct< 34; females Hct< 32) or contraindication to donating blood.
22. Poorly controlled hypertension or systolic blood pressure > 140 on repeat measurement in the last 3 months, on more than one occasion.
23. Significant myocardial disease (e.g., current myocarditis or reduced left ventricular ejection fraction below the lower limit of normal) or diagnosed coronary artery disease.
24. History of cardiac arrhythmia that needs to be medically treated.

25. History of psychotic symptoms (e.g., hallucinations, delusional thinking) in the prior 3 months.
26. History of seizures, abnormal electroencephalogram or brain damage with significant persisting neurological deficit in the past 3 months or currently on anti-seizure medications
27. Significant respiratory disease requiring oxygen.
28. Exposure to any immunomodulatory drug (including maraviroc) in the 12 weeks prior to study.
29. Prior or current use of experimental agents used with the intent to perturb the HIV-1 viral reservoir in the 12 weeks prior to study.
30. Pregnancy. A serum pregnancy test will be performed. If this test is positive, the participant will not be allowed to enter the study since body changes occurring during pregnancy will alter the study results.
31. Recent vaccination within the last 2 weeks prior to study baseline visit. Routine or standard of care vaccinations (such as SARS-CoV-2, influenza, pneumococcal, and meningococcal vaccinations) are allowed but must be administered greater than 14 days prior to baseline study visit. For SARS-CoV-2 vaccination, the last dose must be administered at least 14 days prior to baseline study visit.

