8.2 Blinding

The order in which participants complete the two treatment phases (i.e., oral methamphetamine and placebo) will be unknown to both the participants and the PI/study team. Both the oral methamphetamine and placebo will be prepared in identical capsules by the UCSF CTSI investigational pharmacist, out of sight of the study participant, study coordinator, and study site PI and administered to the participant to maintain double blinding. The investigational pharmacist will randomize each participant according to the methods described above. In the event that participant experiences an adverse event that requires the identity of the study drug be revealed, the PI will be able to contact the investigational pharmacist to break the blind. In the event that a participant blind is broken, the study PIs will determine the impact upon the un-blinded participant's continued participation in the study and if a replacement participant is needed on a case-by-case basis.

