9.3.6 Urine qualitative toxicology

Urine qualitative toxicology testing will be performed at baseline, screening, treatment day, and post-24 hours and post-day 31 after treatment day using a liquid chromatography high mass resolution tandem mass spectrometry (LC-HRMS) method⁶⁷ that allows for the identification of drugs and their metabolites in one assay that has enhanced sensitivity/specificity compared to traditional drug screening immunoassays using LC-MS/MS. Prior to analysis, urine samples will be extracted using matrix dilution method, respectively. The data can be retrospectively analyzed for drugs and metabolites of interest given the untargeted acquisition method, with data collected for all compounds within the mass range of 50-700 daltons. The method has been fully validated for the qualitative detection of 250 drugs and metabolites with lower limits of detection (LLOD) ranging from 0.1 – 50 ng/mL.

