12 PROTOCOL VIOLATIONS

A protocol violation occurs when the participant or the study investigator fails to adhere to significant protocol requirements affecting the inclusion, exclusion, participant safety and primary endpoint criteria. Protocol violations for this study include, but are not limited to, the following:

- Failure to meet inclusion/exclusion criteria
- Use of a prohibited concomitant medication

Failure to comply with Good Clinical Practice (GCP) guidelines will also result in a protocol violation. The Principal Investigator will determine if a protocol violation will result in withdrawal of a participant.

When a protocol violation occurs, it will be discussed with the investigator and a Protocol Violation Form detailing the violation will be generated. A copy of the form will be filed in the site's regulatory binder and in the Sponsor's files.

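### The MA-use exclusion extends to post-dose samples: 24-hour urine can show outside use only after placebo, and judging it needs the allocation that the deciding PI does not have

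*Combined protocol and SAP*

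**What the plan says.** Section 6.3, and the synopsis in the same terms, exclude anyone with MA use not explained by study drug, "based on urine, hair, or serum MA measurements collected at baseline and follow-up study visits". Section 6.2 requires participants to be able to "maintain the inclusion/exclusion criteria" over the full 146 days.

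Section 12 lists "Failure to meet inclusion/exclusion criteria" as a protocol violation and adds: "The Principal Investigator will determine if a protocol violation will result in withdrawal of a participant". Under section 12.4, a participant who withdraws from treatment is replaced only if this happens before the last dosing day.

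On sampling, section 9.3.6 says: "Urine qualitative toxicology testing will be performed at baseline, screening, treatment day, and post-24 hours and post-day 31 after treatment day". It does not say whether the treatment-day urine is taken before or after the dose. Section 9.3.5 gives no times for serum or breath MA, and section 9.3.7 gives none for hair MA.

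On blinding, section 8.2 says the order of treatments "will be unknown to both the participants and the PI/study team". Two parties may know the allocation: the pharmacist ("The investigational pharmacist will randomize each participant according to the methods described above") and, under section 13, the Safety Monitoring Committee (SMC).

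On analysis, section 14.1 names who will analyse the data but defines no analysis set. Section 14.4 and the synopsis list stimulant exposure found in urine as a potential covariate.

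**The concern.** An eligibility criterion normally acts before randomisation and so cannot depend on treatment. This one also acts on samples taken after dosing, and the study drug is the very substance being tested for. Two problems follow.

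- **Unequal action by treatment.** A positive early post-dose urine is uninformative after MA but incriminating after placebo. Any withdrawals it prompts would come from placebo phases, so who remains could depend on treatment received.
- **Conflict with the blind.** Whether a positive is due to study drug cannot be decided without knowing what was given. The PI decides on withdrawal, is the primary medical monitor (section 10.3) and decides on further drug administration (section 10.4). In a two-phase crossover, learning one phase's treatment discloses the other.

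**Working it through.** **1. When the criterion acts.** The order is randomised before the first dose. The 24-hour and Day 31 samples of both phases, and every sample of the second phase (starting Day 77, section 8.1), therefore come after randomisation.

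**2. Study drug remaining.** Section 8.3.1 gives 10 mg, then 15 mg two hours later, with a half-life of 4-5 h. The fraction left after t hours is 2^(-t/half-life). Assume complete absorption and count 24 h from the first dose:

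- Half-life 4 h: 10 × 2^(-24/4) + 15 × 2^(-22/4) = 0.16 + 0.33 = 0.49 mg
- Half-life 5 h: 10 × 2^(-24/5) + 15 × 2^(-22/5) = 0.36 + 0.71 = 1.07 mg
- Day 31: 31 × 24 / 5 = 149 to 31 × 24 / 4 = 186 half-lives, so effectively nothing

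**3. Would 24-hour urine be positive?** Section 8.3.1 puts 62% of drug in urine within 24 h, one third of it intact. Apply 0.62 / 3 = 0.207 to the elimination rate, 0.693 / half-life × amount left:

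- 4 h: 0.693 / 4 × 0.49 mg × 0.207 ≈ 17 µg/h
- 5 h: 0.693 / 5 × 1.07 mg × 0.207 ≈ 31 µg/h

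Urine output is not in the documents. Assuming 1.5-3 L/day (62.5-125 mL/h), intact MA is roughly 140-490 ng/mL. The highest detection limit quoted in section 9.3.6 is 50 ng/mL, so a positive is expected across that range.

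**4. Reading by treatment.**

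| Sample | MA phase | Placebo phase |
|---|---|---|
| Urine, 24 h | Positive expected; outside use masked | Any positive counts as outside use |
| Urine, treatment day, if post-dose | As above | As above |
| Urine, treatment day, if pre-dose | Informative | Informative |
| Urine or serum, Day 31 | Informative | Informative |
| Serum, 24 h | Not shown: no sampling time or distribution volume given | Informative if sampled |
| Hair MA | Cannot be assessed: no time or detection window | Cannot be assessed |

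**5. Replacement.** A participant withdrawn on a 24-hour placebo result in the first phase has not reached the last dosing day and is replaced. In the second phase that day has passed and section 12.4 provides no replacement.

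**6. Cost of an unreplaced loss.** First the plan's own figure (section 14.5): N = 10, SD 0.6 log10, alpha 0.05. Take SD as that of the within-person difference and use a two-sided paired t-test. Power is the probability that a noncentral t with n − 1 degrees of freedom and noncentrality (difference / 0.6) × √n exceeds its critical value. At 0.6 log10 and n = 10 the noncentrality is 3.16 and power is 0.803, which reproduces the stated 80%.

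| n | Power at 0.6 log10 | Power at 0.5 log10 |
|---|---|---|
| 10 | 0.803 | 0.651 |
| 9 | 0.748 | 0.593 |
| 8 | 0.681 | 0.528 |

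The numbers lost are assumptions; the documents give no rate of outside use.

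**The case against.** The best reply is that nothing here need happen.

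- Withdrawal is at the PI's discretion, and participants who stop treatment are encouraged to complete remaining visits (sections 10.3 and 11.1).
- The urine-stimulant covariate makes sense only if some exposed participants are analysed.
- The pharmacist or SMC could read the results. Only CD4/CD8 counts and viral load are described as real-time (section 9.3.1), and section 9.3.6 notes that urine data can be analysed retrospectively.
- Outside use should be uncommon: participants have no MA use disorder, are tested at entry and are observed on dosing days.

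Most of this stands, and it rules out several stronger readings. A reader might infer that the rule automatically removes participants, or their data; no text says so. A reader might infer that blinded staff must be shown revealing results; the accurate statement is that no reader and no firewall are specified. A reader might see a difference between first and second periods; the difference is between MA and placebo. That a treatment-day result discloses the sequence holds only if the sample is post-dose. Counting each removal as a tenth of the sample ignores replacement before the last dosing day.

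What survives is the rule as written. Discretion does not cure it, because the discretion would be used on results that mean different things by treatment. The covariate and the exclusion point in opposite directions and are not reconciled. If the results were read only after the study, the follow-up part of the criterion could not work as an exclusion at all.

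**Conclusion.** The point holds as a defect in the rule, not as a demonstrated bias. The MA-use exclusion extends past randomisation. For 24-hour urine, and treatment-day urine if post-dose, it can detect outside use only in the placebo phase. Applying it there requires an allocation withheld from the person who decides on withdrawal. Neither an unblinded reader nor an analysis set resolves this.

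The size is unknown because no rate of outside use is given. One unreplaced loss would take power at 0.6 log10 from 0.80 to 0.75, and two would take it to 0.68, with SD 0.6 read as the SD of the within-person difference. The expected positive urine rests on the plan's half-life and elimination figures and the assumed urine output. The documents do not support extending the point to Day 31 urine or serum, and they do not show it for 24-hour serum or hair.

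**What to change.** - **Synopsis and 6.3:** limit the eligibility criterion to samples taken before randomisation.
- **12 and 14.1:** record later non-study MA exposure as a reported deviation, define a primary analysis set of all dosed participants, and add a sensitivity analysis that excludes or adjusts for affected phases. State how the covariate in 14.4 relates to this.
- **9.3.5 and 9.3.6:** state whether treatment-day samples are pre- or post-dose. Send post-dose treatment-day and 24-hour MA results (serum, breath, urine) only to the investigational pharmacist or SMC, and withhold them from the blinded team until database lock, except for safety unblinding. Day 31 urine and serum and second-phase pre-dose results need not be withheld.

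Whether a positive result before the second phase affects further dosing is a clinical matter. The sponsor should reconcile sections 6.2, 6.3 and 12 on it.

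The cost is a few wording changes and one laboratory reporting instruction, with no change to visits or sample size. The small downside is that a few contaminated phases stay in the primary analysis, where the sensitivity analysis will show their influence.
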